Official Title:	Pilot Trial to Evaluate Blood and Imaging Based Biomarkers for Aromatase Inhibitor Induced Musculoskeletal Syndrome
NCT number:	NCT03665077
Document Type:	Study Protocol and Statistical Analysis Plan
Date of the Document:	AIMSS IIT Protocol v4.0 12-2-2020

STUDY TITLE: Pilot Trial to Evaluate Blood and Imaging Based Biomarkers for Aromatase Inhibitor Induced Musculoskeletal Syndrome

Protocol Version 1 Dated October 6, 2017

Protocol Version 2 Dated May 14, 2018

Protocol Version 3 Dated October 28, 2019

Protocol Version 4 Dated December 2, 2020

Principal investigator:

[name], MPH

Associate Professor

The University of Arizona Cancer Center
[name]
[name]
P- [contact]
F- [contact]
[contact]

Co-Principal Investigator:

[name]

Assistant Research Professor

Department of Nutritional Sciences
The University of Arizona Cancer Center
[contact]

Statistician

[name]

Professor of Biostatistics

Director of Biostatistics Shared Resource

Funding: University of Arizona Cancer Center

Protocol Synopsis

Title of Study: Pilot Trial to Evaluate Blood and Imaging Based Biomarkers for Aromatase Inhibitor Induced Musculoskeletal Syndrome (AIMSS)

Hypotheses: Baseline plasma oxylipin profiles can be used to predict who is at risk for developing AIMSS.

Primary Objectives:

- To compare baseline oxylipin levels in women that do vs. those that do not develop AIMSS

Secondary Objectives:

- To correlate changes in oxylipin panels with changes in tendon stiffness
- To correlate changes in levels of oxylipins with changes in pain scores through 6-month AI treatment.

Study design: This is a prospective single arm study enrolling patients (n = 35) with breast cancer scheduled to start adjuvant hormonal therapy. Patients would have completed all their primary treatments (surgery± radiation therapy) and are scheduled to start their adjuvant hormonal therapy. They get baseline blood drawn for oxylipins. They start adjuvant anastrozole and have blood drawn at 3mths and 6mths for measurement of oxylipins.. This is a pilot trial to evaluate blood biomarkers. Once pilot data is analyzed, goal is to apply for funding for a larger trial to further evaluate and validate these biomarkers

Study Center: Banner – University Medical Center, University of Arizona Department of Medical Imaging, University of Arizona Cancer Center-North Campus, University of Arizona Cancer Center-Orange Grove Campus, Tucson, AZ

Number of Patients: We plan to accrue a total of 35 patients into this prospective single arm trial to have 20 evaluable patients for analysis

Main Criteria for Inclusion/Exclusion:

Inclusion Criteria

To be eligible for this trial patient must

1. Be capable of understanding the investigational nature of the study and all pertinent aspects of the study
2. Be capable of signing and providing written consent in accordance with institutional and federal guidelines
3. Have a histologically-confirmed diagnosis of breast cancer
4. Be willing and able to comply with scheduled visits, treatment plan

5. Age \geq 21 years
6. Post-menopausal women with 1st event of ER+ early stage breast cancer (0-3)
7. Completed definitive therapy (surgery \pm radiation)
8. Candidates for adjuvant AI therapy

Exclusion criteria

Patients who fulfill any of the following criteria will be excluded from the study:

1. Have received adjuvant or neo-adjuvant chemotherapy
2. Prior endocrine therapy (AI or tamoxifen)
3. History of rheumatoid arthritis or other autoimmune arthritis
4. Daily non-steroidal anti-inflammatory drug (NSAID) use (except for daily aspirin use)
5. Current use of daily corticosteroids or immunosuppressive therapies

Intervention:

Statistical analysis

Statistical Considerations: This is a pilot study to estimate the values needed to design a larger study. The primary objectives are to estimate the baseline oxylipin levels in patients who develop with AIMSS vs. those who do not develop AIMSS. Analysis will be based on descriptive statistics and 95% confidence intervals for each group. Although we will not formally test for differences between the two groups, we will estimate the difference with a 95% confidence interval to inform the design of a larger study.

The secondary objectives are to correlate changes in oxylipin levels with changes in pain scores. These analyses will be based on all 20 women, irrespective of whether they develop AIMSS.

Feasibility Issues: From 2015 to 2016, ~40 patients were started on adjuvant anastrozole therapy who meet our eligibility criteria. Thus, we anticipate accrual of 2-3 patients per month and completion of accrual this pilot study within 8-12 months of study initiation. Based on previously published studies, it is expected that 50% of women initiating AI will develop AIMSS within one year, with most women experiencing symptoms by 2 months.¹⁷ Women who discontinue use of anastrozole before the 6 month visit will complete all measurements at the time that they switch to another AI and come off study.

[name] and the research personnel will be conducting monthly meetings to review patient accrual data, address any barriers to accruals and resolve them in a timely manner. [name] will be overseeing the oxylipin data analysis.

STUDY CALENDAR

			Treatment -Anastrozole	
	Screening	Pre-Treatment	3mths	6mths
Informed Consent	X ^a			
History and Physical Exam	X ^a			
Collection of Blood for biomarker analysis		X ^{b,d}	X ^{c,d}	X ^{c,d}
Questionnaires		X ^b	X ^c	X ^c

- A- Performed within 28 days of trial entry
- B- May be collected/Performed any time prior to starting anastrozole (can be on the same day)
- C- Can be done within 28 day window (\pm) of the time point
- D- Labs have to be fasting

TABLE OF CONTENTS

	Page
Protocol Synopsis	2
1. Introduction	6
2. Study Objectives	10
3. Study Design	10
4. Selection of Patients	10

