This is a prospective single arm pilot study enrolling patients (n = 35) with breast cancer scheduled to start adjuvant hormonal therapy. Patients would have completed all their primary treatments (surgery±radiation therapy) and are scheduled to start their adjuvant hormonal therapy. At baseline, patients will undergo a blood draw. They will start adjuvant anastrozole and have blood drawn at 3 and 6 months for oxylipins. This is a pilot trial to evaluate oxylipins as blood biomarkers of AIMSS.

4. Selection of patients

Number of Patients: We plan to accrue a total of 35 patients with breast cancer into this prospective single arm pilot trial with the goal of having data from 20 evaluable patients.

Main Criteria for Inclusion/Exclusion:

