5.6 Follow Up

Patients will not be followed for this study after completion of the 6 mths blood draw, study questionnaires. However, they will continue to follow-up with their treating physician per standard of care.

6. Criteria for Evaluation

The primary endpoint is comparing baseline oxylipin levels for patients who develop AIMSS vs. those who do not develop AIMSS. For this pilot trial of 20 evaluable patients we expect 10 patients to develop AIMSS and 10 who do not develop AIMSS. The goal is to prospectively evaluate for any baseline levels in both groups and for changes in oxylipin panels.

7. Statistical Considerations:

This is a pilot study to estimate the values needed to design a larger study. The primary objectives are to estimate the baseline oxylipin levels in patients who develop AIMSS vs. those who do not develop AIMSS. Descriptive statistics and 95% confidence intervals will be computed for two baseline oxylipin levels (PGE₂ and 12-HETE) for each group. Based on clinical observation, it is expected that 50% of the women will develop AIMSS. Ten patients in each group will allow us to estimate the 95% confidence interval with width 1.4 times the observed standard deviation. Although we will not formally test for differences between the two groups, we will estimate the difference between the means with a 95% confidence interval, to inform the sample size justification for a larger study.

The secondary objectives are to correlate changes in oxylipin levels with changes in pain scores. These analyses will be based on all 20 women, irrespective of whether they develop AIMSS. We expect that only a small number of women may switch to another AI due to the development of AIMSS. For these women, we will use the values obtained at the time of the switch. Linear regression will be used to estimate the change in pain scores (as measured by the BCPT-MS) versus changes in PGE₂, 12-HETE. Additionally, we will control for changes in depression levels as measured by the PHQ-9. This model will allow us to estimate the effects of each of the oxylipin measures adjusted for depression in a single model.

8. Data and Safety Monitoring Plan

The University of Arizona Cancer Center Data and Safety Monitoring Board (DSMB) has determined that this study falls into the low risk category with regards to DSMB oversight or QA/QC Program monitoring, per the current University of Arizona Cancer Center Data and Safety Monitoring Board (DSMB) Charter

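### Does the 8-12 month accrual forecast need correcting, given that 35 patients at 2-3 per month take 11.7-17.5 months?

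*Combined protocol and SAP*

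**What the plan says.** The accrual forecast stands in the Protocol Synopsis under Feasibility Issues: "we anticipate accrual of 2-3 patients per month and completion of accrual this pilot study within 8-12 months of study initiation". The sentence before it gives the basis: about 40 patients who would have been eligible started anastrozole from 2015 to 2016. The text does not say whether this covers 12 or 24 months.

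The enrolment target is the same wherever it appears. The synopsis gives it under Study design ("This is a prospective single arm study enrolling patients (n = 35) with breast cancer scheduled to start adjuvant hormonal therapy") and under Number of Patients ("We plan to accrue a total of 35 patients into this prospective single arm trial to have 20 evaluable patients for analysis"). Section 3 repeats it ("This is a prospective single arm pilot study enrolling patients (n = 35) with breast cancer"), as does Section 4 ("We plan to accrue a total of 35 patients with breast cancer into this prospective single arm pilot trial").

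Three other places bear on whether the forecast is used for anything:

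- Feasibility Issues says that "research personnel will be conducting monthly meetings to review patient accrual data", and that barriers to accrual will be dealt with.
- Section 6 sets the analysis size: "For this pilot trial of 20 evaluable patients we expect 10 patients to develop AIMSS and 10 who do not develop AIMSS". Section 7 bases its confidence-interval width on those ten women per group.
- Section 8 lists an inadequate pace of enrolment among the circumstances in which the principal investigator may end the study early. It gives no figure.

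**The concern.** One sentence gives both a rate and a duration, and with the stated target of 35 the two do not fit. A reader who divides 35 by the stated rate gets a period that starts about where the stated one ends.

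This could matter for monitoring. It is the only numerical accrual forecast in the plan, and accrual is reviewed monthly. A study recruiting exactly at its stated rate could appear late: at month 12 it would have 24 of 35 patients at 2 per month, or 30 of 35 at 2.5 per month. Section 8 allows termination for slow enrolment without a number, so this forecast is the only benchmark to hand. The next step also waits on the pilot data: "Once pilot data is analyzed, goal is to apply for funding for a larger trial".

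The serious version of the worry is that someone might close accrual by the calendar at 12 months. That could leave fewer than the 20 evaluable women on whom the precision statement rests.

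**Working it through.** **Inputs.** Target N = 35 enrolled, to give 20 evaluable (synopsis, Sections 3 and 4). Rate r = 2-3 per month and period 8-12 months (Feasibility Issues). Historical base of about 40 eligible patients, 2015 to 2016 (Feasibility Issues).

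**Step 1: reproduce the stated period.** Duration = N / r.

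| N | r = 3 | r = 2.5 | r = 2 |
|---|---|---|---|
| 35 (enrolment target) | 11.7 months | 14.0 | 17.5 |
| 20 (evaluable only) | 6.7 | 8.0 | 10.0 |
| 24 | 8.0 | 9.6 | 12.0 |

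The stated 8-12 months is not reproduced with 35 or with 20. It is reproduced exactly with 24, but no target of 24 appears in the documents, so where the window came from is unknown. The 20-patient reading overlaps the window over 8-10 months, but it does not fit the text, which counts accrual as 35 enrolled to obtain 20 evaluable.

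**Step 2: size of the gap.** Low end: 11.7 - 8 = 3.7 months. High end: 17.5 - 12 = 5.5 months. In ratio, 11.67/8 = 17.5/12 = 1.46, so the derived period is 46% longer at each end. The two ranges share only 11.7-12 months.

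**Step 3: rate needed for the stated period.** 35/12 = 2.92 per month for 12 months, inside the stated range but at its top. 35/8 = 4.38 per month for 8 months, outside it.

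**Step 4: does the historical base settle it?** This depends on an assumption about the length of the period.

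- If 24 months: 40/24 = 1.67 per month, below the stated 2-3. Then 35/1.67 = 21 months, even if every eligible patient enrols.
- If 12 months: 40/12 = 3.33 per month. Then 35/3.33 = 10.5 months, inside 8-12, but only if every eligible patient enrols.

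The base therefore supports a period well above or comfortably inside the stated one, depending on the assumption. It cannot show whether the rate or the period is wrong.

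**Step 5: what depends on 8-12 months?**

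- *Precision.* The interval width in Section 7 is a multiple of the standard deviation set by ten women per group. Time does not enter.
- *Sample size.* The target is a count of 35, with no calendar closing date.
- *Early stopping.* Section 8 leaves slow enrolment to the principal investigator's judgement, with no rate or date.
- *Follow-up.* Each woman is observed for 6 months from her own start of anastrozole, whatever the length of accrual.

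**Step 6: the damaging scenario.** Suppose accrual were closed at month 12, and suppose the plan's own evaluable fraction of 20/35 applied. At 2 per month: 24 × 20/35 = 13.7 evaluable. At 2.5 per month: 30 × 20/35 = 17.1. Both fall short of 20. But no provision in the plan closes accrual at month 12, so this loss does not follow from the inconsistency.

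**The case for a change.** The case for correcting the sentence is sound on its facts. The target is stated consistently, the division is elementary, and no ramp-up is described; a slow start would in any case lengthen accrual. The edit would cost one sentence and no patients, visits or assays. With no figure in Section 8 for acceptable enrolment, the investigator may well look to this forecast when judging progress.

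The arithmetic stands in full. The consequence is weaker. The statement is an expectation built from two approximate ranges, and one combination of them (3 per month, 11.7 months) satisfies both. The monthly meetings are there to look at accrual and remove barriers; the plan does not say they compare progress with 8-12 months. The follow-on funding application has no date in the documents to slip against.

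The obvious correction is also not well founded. Restating the period as about 12-18 months takes 2-3 per month as sound. If the historical period is 24 months, that rate exceeds the whole eligible pool of 1.67 per month, and the new period would be too short as well. A proper correction needs the length of the historical period and an expected consent fraction, and the documents give neither.

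Finally, version 1 is dated October 2017 and version 4 December 2020, about 38 months apart. If the study opened under an early version (an assumption, since no initiation date is given), the forecast window had passed before the current version was issued.

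**Conclusion.** The rate, the period and the target do not agree. This is a slip in a feasibility forecast, and correcting it brings no gain to the trial. No estimate, interval, enrolment target or stopping decision is tied to the stated period, so it can stand. Anyone reading accrual reports can divide the remaining patients by the observed monthly rate, which is a better guide than either forecast figure.

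This conclusion rests on two points: accrual continues to 35 patients and is not closed by date, as the documents describe, and about 20 women prove evaluable. If accrual were in practice cut off at 12 months, the shortfall would matter, but the cause would be that decision and not this sentence.

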Adjuvant aromatase inhibitor (AI) therapy is the recommended first-line adjuvant treatment for postmenopausal women with estrogen receptor positive (ER+) breast cancer based on improved disease-free survival (DFS) compared to tamoxifen in randomized control trials. More recently extended adjuvant AI therapy (for 10 years) has been shown to improve DFS when compared to placebo in women who completed 5 years of standard AI therapy.^{1,2} However, AI therapy has been associated with significant, activity-limiting musculoskeletal symptoms including arthralgia, myalgia and joint stiffness or AI-induced musculoskeletal syndrome (AIMSS).³ AIs block estrogen synthesis and induce menopausal symptoms that are particularly severe in younger patients.^{4,5} Musculoskeletal complaints are among the most commonly reported and debilitating side effects of adjuvant AI therapy;⁶ findings that are supported by observations in aromatase knockout mice which exhibit increased pain responses.⁷ Among women with arthralgia syndromes at initiation of AI therapy, half report symptom exacerbation. Joint-related symptoms manifest early after initiation of AI therapy with worsening of symptoms up to 1 year post-initiation of AI.^{8,9} AIMSS impairs ability to perform activities of daily living as well as work-related tasks as the most commonly affected joints are hands, knees and hips.^{10,11} In a survey conducted by Breast Cancer Action, 27% of respondents reported that they had discontinued adjuvant AI use because of adverse effects (AE), with AIMSS being the leading AE.¹² In a cohort study in California, 61% of patients on AIs developed joint and/or bone pain resulting in discontinuation of therapy in 20% of patients.¹³ In a recent study, full adherence, defined as full duration and optimal schedule, was observed for only 49% of breast cancer (BC) patients prescribed any hormone therapy (HT) and was related to higher mortality in those who discontinued [Hazards Ratio (HR) = 1.26 (Confidence interval (CI) 1.09–1.46)] or were non-adherent to HT [HR = 1.49 (CI 1.23–1.81)].¹⁴ This study is concerning and consistent with clinical trial evidence from prior tamoxifen studies showing higher recurrence rates and worse outcomes with < 5 years or suboptimal HT use.^{15–17} Clearly, there is a need to maximize efficacy and improve tolerance to AIs. Approaches to study interventions that enhance both adherence and response rates for AIs are important research and clinical gaps that must be addressed to reduce death from breast cancer.^{18,19} **A critical first step is to identify those who are at risk of developing AIMSS by developing predictive biomarkers that will provide physicians opportunity for early intervention, thereby improving adherence to AIs. Currently there are no predictive biomarkers available to identify those at risk of developing AIMSS.**

Mechanisms of Aromatase Inhibitor-Associated Pain. The mechanism of AIMSS is not well understood and is grossly understudied. Based on observational data and animal data, it is likely that AIMSS is directly related, at least in part, to a) loss of the anti-nociceptive action of estradiol - resulting in greater sensitivity to stimuli and b) presence of underlying inflammation and the nociceptive activity or pain-inducing response of PGE₂. In aromatase-knockout mice, which lack endogenous estrogen production and serve as an animal model of AI therapy, estrogen deprivation results in a dominance of pro-nociceptive (pain) over anti-nociceptive response mechanisms following noxious stimuli such as formalin injection.²⁰ Results from experimental models to determine the role of estradiol in inflammation and specifically in cyclooxygenase (COX)-mediated PGE₂ are inconsistent and model dependent. Hunter *et al* demonstrated that ovariectomized rats exhibited greater sensitivity to a pain stimulus, as

measured by latency to paw withdrawal following an inflammatory insult.²¹ Serum levels of PGE₂ were increased in these rats, indicating an increase in inflammation. Pain sensitivity was reversed with estradiol replacement but serum PGE₂ levels did not change, indicating a separate mechanism for inflammatory response. The addition of a COX2 inhibitor increased latency to paw withdrawal compared to estradiol replacement alone, indicating a reduced pain response for these animals, and again indicating separate roles for inflammation and estradiol in pain response.²² Using this same model, ibuprofen (a non-steroidal anti-inflammatory drug, NSAID; a COX inhibitor) + estradiol replacement was shown to be more effective in reducing pain than either estradiol or ibuprofen alone.²² Collectively, these results indicate that the loss of estrogen alone does not increase pain by inducing PGE₂; but in the presence of PGE₂-mediated inflammation, estrogen deprivation increases sensitivity to inflammatory pain. **Therefore, if PGE₂ is elevated at baseline, this can predispose women to experience pain upon the depletion of estradiol with the addition of an AI.**

In healthy women, joint and muscle pain worsen with age with greatest increases between 50 - 59 years.^{23,24} New onset of rheumatoid arthritis is also highest in the decade following menopause. Such observations, in combination with extensive experimental studies in animal models, have established estradiol as having both anti-inflammatory and anti-nociceptive properties.²⁴ Increased inflammation with aging, mediated by bradykinin and the pro-inflammatory prostaglandins (PGs), including PGE₂, has been mechanistically linked to hyperalgesia (increased sensitivity to painful stimuli) and allodynia (painful response to what would normally be an innocuous stimulus). Thus, inflammation and injury that stimulate PG release are thought to result in a heightened nociception and allodynia with the decline in estradiol levels with menopause.²⁵

Management of AIMSS in AI Patients. While all 3 third-generation AIs in routine clinical use cause different levels of estradiol suppression,²⁶ toxicity profiles are similar for all of them.²⁷⁻²⁹ Further, many studies show that there is no correlation with degree of estrogen depletion and pain in women on AI, regardless of AI type.^{30,31} Differences between agents in terms of quality of life (QOL) and tolerability are very important when selecting the optimal therapy for individual patients. Randomized clinical trials comparing tolerability and QOL between letrozole and anastrozole did not show any significant differences between the QOL scores. They did report that subjects who were intolerant to one AI were nonetheless able to tolerate another agent.^{32,33} Other studies have also demonstrated that switching AIs can result in improvements of AIMSS.^{33,34} This is a significant finding given that—despite AIs having similar toxicity profiles—AIMSS can sometimes be managed by switching AIs.

AIMSS management is an area of active research interest. For patients developing AIMSS, there is evidence that acupuncture^{35,36} high dose vitamin D³⁷ or exercise³⁸ might help in alleviating their symptoms. Yet results are not always consistent and are limited by small numbers of participants. Recently, a randomized, placebo-controlled study reported a 50% decrease in AIMSS symptoms with ω-3 fatty acid supplementation; however, this change was not significantly different when compared to the placebo arm.³⁹ Retrospective clinical data reported a significantly decreased recurrence and longer disease-free survival in obese women with ER+ tumors who take NSAIDs.⁴⁰ Anti-inflammatory medications like NSAIDs or COX2 inhibitors might alleviate arthralgia and myalgia but have gastrointestinal and cardiac side effects. Currently, for a patient who develops AIMSS, routine management involves i) pain control with NSAID's or other pain medicines, ii) stopping and switching to a different AI or tamoxifen, iii) stopping adjuvant hormonal therapy completely or iv) referral to orthopedic surgeon based on

symptom severity. It is important to realize **not all patients who take AIs develop AIMSS**. It is crucial to determine which patients are at risk so that preventative strategies can be implemented early on to improve adherence to AI therapy and eventually decrease breast cancer relapse and death. **Identifying at-risk subjects by developing predictive biomarkers is a critical unmet need in AIMSS.**

Pain and Oxylipin Cascade. While PGE₂ is the best-studied metabolite of arachidonic acid metabolism, arachidonic acid and other polyunsaturated fatty acids (i.e., ω-3 and ω-6) are also metabolized by the lipoxygenases (LOX) and cytochrome P450 (CYP) enzymes, yielding distinct sets of metabolites with their own biological activities. Collectively, these COX, LOX and CYP metabolites are called oxylipins. The oxylipin metabolites of ω-3 and ω-6 fatty acids comprise over 100 metabolites, each of which exhibit potent biological effects, including acting as modulators of inflammation (pro- and anti-) as well as activators of angiogenesis and mediators of hyperalgesia and allodynia.⁴¹⁻⁴³ Recently, it has been demonstrated that there is cross-talk between the estrogen receptor and LOX-mediated oxylipins,⁴⁴ and that AIs can upregulate the CYP450 pathway and downstream epoxyeicosatrienoic acids *in vitro*.⁴⁵ It is well established that downregulation of PGE₂ production through inhibition of COX2 alleviates inflammatory pain. Preliminary evidence implicates both the CYP450 and LOX pathways in the development of tendinopathy.^{46,47} Two earlier clinical trials showed that 12-hydroxyeicosatetraenoic acid (12-HETE) was significantly correlated with pain in menstruating women,^{48,49} suggesting interplay between 12-HETE and hormonal changes. Our preliminary data in AI-treated women participating in an intervention with sulindac (a non-selective COX2 inhibitor) suggests involvement of 12-HETE and other LOX metabolites in AIMSS (see **Approach**). If we successfully show that oxylipins are pathogenic in the development of AIMSS, there are already pharmacologic agents available (COX and LOX inhibitors) or in development (CYP pathway inhibitors) that can be implemented to target these pathways⁵⁰ and alleviate symptoms, with the ultimate goal of improving AI adherence in clinical practice. As cited above, interventional clinical trials have been inconsistent, and there have been no studies that have determined predictive blood-based biomarkers for AIMSS in order to guide optimal subject selection to study appropriate interventions.

Table 2: Relationship between oxylipins and pain in 10 breast cancer patients on AI^a

Enzyme	Oxylipin	How much pain interferes with walking ability	
		R ²	P-value
COX	PGE ₂ ^c	0.11 ^d	0.36
LOX	12-HETE ^c	0.44	0.04
LOX	15-HETE	0.25	0.15
LOX	11-HETE	0.21	0.18
LOX	9-HETE	0.25	0.14
LOX	8-HETE	0.21	0.19
LOX	5-HETE	0.09	0.41

^aOxylipins quantified in plasma drawn after a 3 month observation period

^bQuestion from the Brief Pain Inventory Short Form (BPI-SF) on a scale of 1-10.

^cTarget oxylipins: Prostaglandin E₂ (PGE₂) and 12-Hydroxyeicosatetraenoic acid (12-HETE)

^dAll R² values are positive correlations between indicated oxylipin level in plasma and score from BPI-SF

Preliminary Data:

Oxylipins:

[name] is institutional PI of an ongoing clinical trial to determine the effect of sulindac (an NSAID) on breast density and pain in women that have been stable on AI for 6 months. Participants receive sulindac (150 mg BID) for 12 months.

Table 1: Plasma levels of target oxylipins in 10 breast cancer patients on AI^a

	Plasma (nM) ^b
PGE ₂ ^c	0.35 (±0.47)
12-HETE ^d	65.2 (±53.4)

^aOxylipins measured in plasma collected after a 3-month observation period

^bData presented as: mean (±SD)

^cPGE₂: prostaglandin E₂

^d12-HETE: 12-Hydroxyeicosatetraenoic acid

Plasma and urine samples are collected before and after a 3-month observation period (months -3 and 0), and after 3, 6, 9, and 12 months on sulindac.

Participant demographics. This study is currently conducted in post-menopausal women diagnosed with ER+ breast cancer. Inclusion and exclusion criteria for this study regarding breast cancer history are the similar as the proposed work except that participants in the Sulindac trial must have been stable on AI for 6 months and exclusion criteria for this trial also includes active smokers, history of diabetes mellitus, uncontrolled hypertension, GI ulcers and bleeding diathesis .

Oxylipins in women on AI. We have conducted oxylipin profiling in the plasma and urine in 10 women after the 3 month observation period (selected based on availability of samples). We quantified 92 total oxylipins in plasma and 87 in urine with good reproducibility. PGE₂ levels were similar to the ranges previously reported in plasma of other breast cancer patients.⁸⁶⁻⁸⁸ Levels of target oxylipins after a 3-month observation period (PGE₂ and 12-HETE) in women on AI are presented in **Table 1**.

Pain and oxylipins. How much pain interferes with daily activities such as walking ability was evaluated using the Brief Pain Inventory Short Form (BPI-SF). Oxylipin levels after a 3 month observation period were correlated with questionnaire items at the same time-point. **Table 2** presents the results from linear regression comparing how much pain interferes with walking ability and selected plasma oxylipin levels in 10 women stable on AI. PGE₂ levels were not correlated with how much pain interfered with walking ability. However, plasma levels of the LOX metabolite, 12-HETE, were significantly correlated. While not statistically significant, a similar pattern was observed across multiple LOX metabolites. This trend could still be observed in only 10 participants with overall low scores for how much pain interferes with walking ability (mean \pm SD; 2.48 \pm 2.45), which suggests a role for the LOX arm of the oxylipin pathway in the development of AIMSS. There was no correlation (positive or negative) with CYP450-derived metabolites and pain scores (data not shown).

While these results are promising and suggest that the LOX pathway may be related to AIMSS, samples from this clinical trial have several limitations. First, participants in this study were stable on AI for at least 6 months. Therefore, there is no true “baseline” to quantify oxylipins levels. Second, hand-specific symptoms, common in AIMSS, were not evaluated. Third, there is no BPI-SF score that specifically addresses AIMSS development. Fourth, while we have presented our preliminary data from the baseline (post-NSAID washout and 3 month observation period) only, women in this study initiate intervention with sulindac (a non-specific COX2 inhibitor). Thus, it is likely that the oxylipin cascade will be modulated by the intervention, and stored samples from this trial will not be appropriate to determine changes in oxylipins related to the natural history of AIMSS. Despite these limitations, these data demonstrate that oxylipins are quantifiable in the plasma of women currently taking an AI, and that they are present in a wide enough range of levels to relate to pain scores.

2. Study Objectives

Primary Objectives:

- To compare baseline oxylipin levels in women that do vs. those that do not develop AIMSS

Secondary Objectives:

- To correlate changes in levels of oxylipins with changes in pain scores through 6-month AI treatment.

3. Study design:

This is a prospective single arm pilot study enrolling patients (n = 35) with breast cancer scheduled to start adjuvant hormonal therapy. Patients would have completed all their primary treatments (surgery±radiation therapy) and are scheduled to start their adjuvant hormonal therapy. At baseline, patients will undergo a blood draw. They will start adjuvant anastrozole and have blood drawn at 3 and 6 months for oxylipins. This is a pilot trial to evaluate oxylipins as blood biomarkers of AIMSS.

4. Selection of patients

Number of Patients: We plan to accrue a total of 35 patients with breast cancer into this prospective single arm pilot trial with the goal of having data from 20 evaluable patients.

Main Criteria for Inclusion/Exclusion:

